6.3.2 Secondary Efficacy Parameters

Pain assessment on VAS for evaluating pain at rest

Ankle pain will be measured using a 100 mm VAS starting with no pain (0 mm) and ending with most severe imaginable pain the patient may imagine in relation to his/her ankle sprain (100 mm).

The patients will be asked after 5 minutes rest to assess their pain themselves on a VAS scale.

Foot and Ankle Ability Measure (FAAM), Activities of Daily Living (ADL)

The FAAM is a validated questionnaire and was developed to meet the need for a self-reported evaluative instrument that comprehensively assesses physical function of individuals with musculoskeletal disorders of the leg, foot, and ankle.

It is a well-established and widely used responsive multidimensional outcome measure with a sensitivity capable of detecting subject-relevant symptoms and clinically significant changes in health in ankle sprain.

The FAAM-ADL/S consists of an ADL (21-item scale) and a sports (S) subscale (8 items) asking study participants to rate their ability to perform specific tasks. The FAAM-ADL/S is a valid and reliable instrument in the public domain (Martin 2005, Carcia et al. 2008).

The possible responses for each item are the following: no difficulty, slight difficulty, moderate difficulty, extreme difficulty, unable to do and not applicable.

In this clinical trial FAAM-ADL will be used. The scoring of the FAAM-ADL will be performed according to the recommendations of Martin et al. 2005.

The response to each item on the FAAM-ADL subscale will be recorded from 4 to 0, with 4 being 'no difficulty' and 0 being 'unable to do'. Responses marked as not applicable will not counted. The scores on each of the items will be added together to get the item score total. The total number of items with a response is multiplied by 4 will get the highest potential score. If all 21 items are answered, the highest potential score will be 84. If one item is not answered the highest potential score will be 80, if two are unanswered the highest potential score will be 76. The total item score will be divided by the highest potential score and then multiplied by 100 to produce the FAAM-ADL score that ranges from 0 to 100. According to the above recommendations the final scores of the FAAM-ADL subscale is to be standardized to a 0 - 100 scale (0 = worst score, 100 = best score).

Time to 50 % improvement of pain measured by VAS

The time to 50 % improvement will be calculated from VAS assessments on pain at rest performed at all patient visits using the percent changes from baseline (recorded at Day 1).

Rescue medication

The rescue medication use will be documented in the eCRF based on the information given in the patient diary and the drug accountability for rescue medication during the study.

6.3.3 Safety Assessments

In this study topical medications are applied for a local disorder where systemic effects are neither expected from the disorder nor from any of the investigational medications given. Due to these reasons, no safety laboratory testing is planned for this study.

Adverse Events

Definition, collection and reporting of adverse events are described in [protocol] section 9.

Vital Signs

Vital signs (heart rate, systolic/ diastolic blood pressure) will be collected and evaluated by comparison of the results obtained pre- and post-treatment.

Physical examination

At screening/ baseline and at final visit a physical examination will be performed. Physical status of cardiovascular, respiratory musculoskeletal and gastrointestinal systems, head and eyes and in addition other abnormalities if applicable will be recorded in the eCRF.

Any clinically significant change observed at the final evaluation of vital signs and physical examination in comparison with baseline has to be evaluated carefully, recorded as AE if abnormal, and a possible causality will be evaluated (see [protocol] section 9.3.2).

7. BLIND DATA TRANSFERS AND QUALITY ASSURANCE

The blind data transfers from the CRO responsible for the eCRF (AMS Advanced Medical Services GmbH) to IDV was performed according to the IDV Data Transfer Guideline Version Final 1.0 from 13 December 2017.

The following data transfers were performed for risk-based centralized statistical monitoring:

- INTERIM TRANSFER:
 - 1. 28.05.2018 (TRAUMED-2018-05-28 01)
 - 2. 26.06.2018 (TRAUMED-2018-06-26 02)
 - 3. 03.09.2018 (TRAUMED-2018-09-03 03)
 - 4. 08.11.2018 (TRAUMED-2018-11-08 04)
 - 5. 15.01.2019 (TRAUMED-2019-01-15 05)
 - 6. 11.03.2019 (TRAUMED-2019-03-11 06)
 - 7. 12.04.2019 (TRAUMED-2019-04-12 07)
 - 8. 13.05.2019 (TRAUMED-2019-05-13 08)
 - 9. 09.09.2019 (TRAUMED-2019-09-09 09)
 - 10. 18.11.2019 (TRAUMED-2019-11-18_10)
 - 11. 14.01.2020 (TRAUMED-2020-01-14 11)
 - 12. 11.07.2020 (TRAUMED-2020-07-11 12)
 - 13. 11.09.2020 (TRAUMED-2020-09-11 13)
 - 14. 10.11.2020 (TRAUMED-2020-11-10 14)
 - 15. 02.12.2020 (TRAUMED-2020-12-02 15)
- SOFTLOCK TRANSFER:
 - o 18.01.2021 (TRAUMED-2021-01-18 16)
 - o 20210113 C1502 Issue Overview FINAL
- HARDLOCK TRANSFER:
 - o 29.03.2021 (TRAUMED-2021-03-29 17)

Based on the hardlock data, patients with major protocol deviations are coded on the base of the definitions in the final Statistical Analysis Plan. The major protocol deviations leading to exclusion from analysis sets as well as the final datasets (analysis populations) are documented on a per patient base in the Appendix of the final Statistical Analysis Plan.

8. CHANGES TO THE PROTOCOL

Preliminary Remark on Substantial Protocol Amendment version 4.0 (February 3, 2020) to Protocol version 3.0

A total of 184 'issue patients', for whom maintenance of blinding procedures may have been compromised, have been identified in 2019 after re-examination of adherence to blinding specifications by the local monitors. Rationale for the re-examination were corresponding findings from site inspections by the German Local Authorities in 2019 (Gesundheitsamt Düsseldorf of German Federal State North Rhine Westphalia, NRW). Re-training and close follow-up control for the sites was implemented to prevent occurrence of further issue cases.

In order to ensure the pre-defined power of the trial for the trial objectives, including the confirmatory test for non-inferiority (Traumed® gel compared to diclofenac gel) based on the Per-Protocol Analysis Set (PP), a sample size enhancement was introduced by means of Protocol Amendment version 4.0 to Protocol version 3.0 for compensation of cases for whom maintenance of blinding procedures may have been compromised.

As specified in C1502 Study Protocol Version 4.0 (3 February 2020) and in the Amendment Summary Document for Substantial protocol Changes (3 February 2020), detailed handling of these problem cases have to be defined in this update of the Statistical Analysis Plan (SAP).

Based on the Blind Data Review Meeting from March 09, 2021 (C1502_MTG_NOTES_BDRM_09MAR2021_20210324), the operational handling as specified in the following section shall ensure the integrity and validity of the trial.

OLD

(Final C1502 Study Protocol Version 4.0, Amendment to Protocol version 3.0)

In order to ensure the data integrity of the trial and to exclude potential bias introduced by partial unblinding, a separate analysis of problematic and non-problematic cases will be conducted with subsequent meta-analytic pooling and test for overall effect and heterogeneity.

Further details will be defined in an update of the Statistical Analysis Plan (SAP).

NEW

(Final BDRM decision)

In order to ensure the data integrity of the trial and to exclude potential bias introduced by partial unblinding, a separate analysis of problematic and non-problematic cases will be conducted. All confirmatory and secondary analyses will be based on the group of non-issue patients. Results of issue patients will be provided separately in the Appendix of the Clinical Trial Report (CTR).

RATIONALE

Blind data review revealed severe deviations of 'issue' cases from 'non-issue' cases, suggesting that compromised cases might constitute a serious risk of bias, preventing pooled analysis.

The multivariate P-values for the comparison of issue cases vs. non-issue cases regarding the three key domains "Baseline", Efficacy", and "RICE", were throughout below 0.0001, thus, suggesting serious structural differences between issue cases and non-issue cases. The rate of major protocol violations was significantly higher in the group of issue cases (11.4%) as compared to non-issue cases (1.9%; P<0.0001). Also the patient's guess on which treatment he/she received was less balanced in the issue group as compared to the non-issue group (patient's guess for the two active treatments: non-issue cases: 39% Traumed vs. 35% diclofenac, issue cases: 42% Traumed vs. 29% diclofenac).

Final BDRM Decision: In order to preserve the integrity and validity of the trial, issue patients will not be included into the pre-planned confirmatory and secondary analyses of the main part of the Clinical Trial Report. While being evaluated for baseline characteristics, efficacy and safety endpoints in the same way as the non-compromised cases, the compromised cases will be reported separately in the Appendix of the Clinical Trial Report (results to be interpreted with care due to the described issues).

As stated before, the sample size was already proactively increased for compensation in case of an exclusion of the issue patients (Protocol Amendment version 4.0 from February 3, 2020 to Protocol version 3.0). The Reason/Justification for Change of Protocol Section 11.4 (Protocol Amendment version 4.0 from February 3, 2020 to protocol version 3.0) was provided in the Amendment Summary Document for Substantial Protocol Changes (SOC document from February 3, 2020):

The enhancement will ensure planned power and validity for evaluating the pre-defined trial objectives also in case that **only non-compromised cases** allow valid and unbiased conclusions ...

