9.6 Evaluations and Endpoints – Safety

9.6.1.1 Operationalizations in Final Protocol

Safety variables are:

- AEs
- other observations related to safety (physical examinations, vital signs).

All safety summaries will be performed on the Safety Analysis Set if not indicated otherwise. For vital signs, no formal testing will be applied to detect imbalances between the treatment groups.

AEs will be presented by MedDRA Preferred Term and System Organ Class in different categories.

Incidence rates of AEs, SAEs and AEs related to investigational product will be reported. The duration of exposure to IMP and the amount of IMP used for the three treatment groups (Traumed® gel, diclofenac gel and placebo gel) will be analyzed.

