9.7 Analysis Populations

9.7.1.1 Operationalizations in Final Protocol

Safety Analysis Set: Randomized patients who receive at least one dose of investigational medication will form the Safety Analysis Set. The Safety Analysis Set will be used for all analyses of safety, tolerability, and background characteristics. For this set, the exposure to IMP will be also analysed.

Full Analysis Set (FAS): The Full Analysis Set is a subset of the Safety Analysis Set consisting of all patients with acute unilateral Grade 1 or Grade 2 sprain of the lateral ankle, for whom both baseline and Day 4 VAS values of pain are available. The Full Analysis Set will be used for the Intent-to-Treat (ITT) analysis.

Per-Protocol (PP) Set: Patients in the Full Analysis Set without major protocol deviations will form the PP Set. The PP Set will be used for the per-protocol analysis of the efficacy parameters. The same efficacy evaluations as in the FAS are planned. Relevant differences between the FAS and PPS will be evaluated in the Clinical Trial Report.

Protocol deviations will be collected during the entire trial and will be classified as minor or major at the Blind Data Review Meeting (BDRM). Protocol deviations that may affect the efficacy outcome of participants will be classified as major. The decision about major protocol deviations and assignments to populations will be documented in the BDRM minutes.

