13.3 Table of Contents for Data Displays (Items of eCRF)

All items of the eCRF will be presented in individual participant data listings and in appropriate summary tables. Standard descriptive summary statistics will be calculated for continuous and semi-continuous variables (i.e., arithmetic mean, standard deviation, standard error of the mean, minimum value, lower quartile, median, upper quartile, maximum value, number of non-missing values). In addition, measures for skewness and kurtosis will be provided for suitable efficacy variables. Categorical data will be presented in frequency tables using counts and their associated percentages. Individual participant data listings will be presented per eCRF item and will be sorted appropriately. Summary tables will be displayed by treatment conditions and visit (if applicable). Where appropriate, the presentation will include changes from baseline. Semi-quantitative and quantitative efficacy data will be additionally visualized by boxplot diagrams. All standardized effect sizes (Mann-Whitney) will be visualized with their corresponding 95%-confidence intervals. All standard statistical tables will be generated applying the standard table layout of the validated statistical package TESTIMATE V6.5.14 (IDV Gauting). Associated meta-data and variable labels are finalized before unblinding All standard scientific figures are generated applying the standard figure layout of the validated scientific package SCIENCEGRAPH V4.9.39 (IDV Gauting).

KLIFO-013.05-A1.02

Data displays will be provided for the following analysis sets:

Chapter Title	Analysis set
Study Patients	A: All patients randomized
Demographic and Other Baseline Characteristics	B: Safety analysis set C: Full analysis set D: Per-protocol analysis set
Treatment Compliance	B: Safety analysis set C: Full analysis set D: Per-protocol analysis set
Visits	B: Safety analysis set C: Full analysis set D: Per-protocol analysis set
Analysis of Efficacy	C: Full analysis set D: Per-protocol analysis set
Analysis of Concomitant/ Supportive Therapies	B: Safety analysis set C: Full analysis set D: Per-protocol analysis set
Analysis of Safety	B: Safety analysis set

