13.4 Clinical Trial Report (CTR) Specifications

13.4.1 Core CTR Specifications

The Core Clinical Trial Report (CTR) will be generated by means of the idv ICH-Study-Report-Manager V2.4.3 within the validated working environment at the department 'Clinical Research/ Biometry' in the institute IDV Data Analysis and Study Planning. The generation is based on the idv CTR template according to idv SOP KLIFO-16.04, the template being finalized before breaking the blind. The following specifications will apply to the CTR:

- Layout is DIN A4 format
- Body text font is Times New Roman 12 pt
- Language is American English (AE)
- CTR Structure is following the idv template according to idv SOP KLIFO-16.04
- CTR protocol sections are cited in original wording (unchanged or in past tense), the same applies to CTR SAP sections
- Scientific tables will be imported with full audit trail via validated pathway of module *idv-Tabellen/-Text*, remaining unchanged after import (original table)
- Scientific figures will be imported with full audit trail via validated pathway of module *idv Science-Graph-Tools*, remaining unchanged after import (original figure)
- Separate tables of content for core text, tables, and figures; generation by ICH-Study-Report-Manager V2.4.3
- CTR Versions:
 - Draft 0.1 (IDV Mock Report, generated before unblinding)
 - o Draft 1.0 (initial IDV CTR version after unblinding)
 - o Draft 1.X (follow-up CTR version after external review)
 - Draft to Final (IDV)
 - o Final (IDV)

13.4.2 Appendices:

- o Title pages generated according to title page of Core Report
- Appendix 1: Individual Patient Listing ('Non-Issue' Cases)
 - Listing of analysis data (validated XLI-export from TESTIMATE V6.5.14 analysis database with variable description by means of TESTIMATE V6.5.14 metadata)
- Appendix 2: Tables and Figures ('Non-Issue' Cases)
 - Tables will be imported with full audit trail via validated pathway of module idv-Tabellen/-Text, remaining unchanged after import (original scientific table)
 - Figures will be imported with full audit trail via validated pathway of module idv Science-Graph-Tools, remaining unchanged after import (original scientific figure)
- o Appendix 3: 'Issue" Cases
 - A. Individual Patient Listing (for specs see Appendix 1)
 - B. Tables and Figures (for specs see Appendix 2)

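### The SAP reports the safety results of the 184 issue patients only in a separate appendix and names no pooled adverse-event table, which conflicts with its own Safety Analysis Set of all dosed patients.

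*SAP*

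**What the plan says.** SAP section 8 reports "A total of 184 'issue patients', for whom maintenance of blinding procedures may have been compromised", identified in 2019. The blind data review decision in that section is that "issue patients will not be included into the pre-planned confirmatory and secondary analyses of the main part of the Clinical Trial Report". It then mentions safety by name: after evaluation for "efficacy and safety endpoints in the same way as the non-compromised cases, the compromised cases will be reported separately in the Appendix", with a caution on interpretation.

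SAP 13.4.2 builds the report on that split. Appendix 1 holds listings for non-issue patients. The tables and figures are in "Appendix 2: Tables and Figures ('Non-Issue' Cases"). Appendix 3 holds listings, tables and figures for the issue patients. Appendix 4 lists the raw data files and is not divided.

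The definitions of the safety population were left as they were:

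- SAP 9.7.1.1, repeating protocol 11.1.1: "Randomized patients who receive at least one dose of investigational medication will form the Safety Analysis Set".
- SAP 9.6.1.1: "All safety summaries will be performed on the Safety Analysis Set if not indicated otherwise".
- SAP 13.3 assigns the safety analysis displays to "B: Safety analysis set".
- SAP 9.7.1.2 limits the confirmatory and secondary analyses to non-issue patients and does not alter the safety set.
- SAP 9.6.1.2 adds only a pointer to the standard descriptive statistics.

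**The concern.** Tolerability and safety of the gel is a stated secondary objective (protocol section 4). If section 8 governs, the AE, SAE and related-AE incidences in the main report come from a subset chosen by blinding status. A reaction that occurred only in an issue patient would then be tabulated only in an appendix that carries a caution. If 9.6.1.1 and 9.7.1.1 govern, the same tables include every dosed patient. A programmer following the SAP could defend either denominator.

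The reasons in section 8 are differences in baseline, efficacy and RICE, the rate of major protocol violations, and the patients' treatment guesses. No safety finding is cited. The protocol elsewhere keeps efficacy and safety exclusions apart. Patients reclassified as Grade 3 up to Day 4 leave the efficacy analysis but stay in the safety analysis (protocol 5.3). For the issue patients, protocol 11.4 names only exclusion from the per-protocol set.

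**Working it through.** **Inputs.** Protocol 11.4: a 1% AE is to be found with 95% probability; 299 Traumed patients needed; 4% drop-out from the Safety Analysis Set; 312 Traumed and 624 in total before enlargement; 404 and 808 after; allocation 2:1:1. SAP section 8: 184 issue patients. Assumption: the 184 split 2:1:1, because the documents give no split by arm.

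**1. The plan's own figures.** The probability of at least one case among n patients is 1 − (1 − p)^n. With p = 0.01, n = ln 0.05 / ln 0.99 = 298.07, rounded up to 299, which gives 95.05%. Then 299 / 0.96 = 311.5, rounded up to 312; 2 × 312 = 624; 624 + 184 = 808. All the stated figures reproduce. The enlargement equals the number of issue patients.

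**2. Size of the issue group.** 184 / 808 = 22.8% of planned patients. On Traumed, 184 / 2 = 92 of 404.

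**3. Treated Traumed patients after 4% drop-out, rounded down.**

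| Group | Randomised | Treated | Chance of at least one 1% AE | Lowest incidence seen with 95% probability, 1 − 0.05^(1/n) |
|---|---|---|---|---|
| Non-issue only | 312 | 299 | 1 − 0.99^299 = 95.0% | 0.997% |
| All exposed | 404 | 387 | 1 − 0.99^387 = 98.0% | 0.77% |
| Issue only | 92 | 88 | 1 − 0.99^88 = 58.7% | 3.3% |

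The chance that a 1% AE appears only among issue patients is 0.99^299 × (1 − 0.99^88) = 0.0495 × 0.587 = 2.9%.

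**4. Sensitivity to the split.** With 78 issue patients on Traumed, (404 − 78) × 0.96 gives 312 treated non-issue patients and 95.7%. With 106, (404 − 106) × 0.96 gives 286 and 94.4%. This range is about two binomial standard deviations either side of 92 (√(184 × 0.5 × 0.5) = 6.8).

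**5. Effect on a common incidence (illustration).** Take 9.5%, the overall AE incidence in the gel arm of the earlier ankle-sprain trial cited in protocol section 3. The 95% half-width, 1.96 × √(0.095 × 0.905 / n), is 3.3 points with n = 299 and 2.9 points with n = 387. If the rate were 9.5% in non-issue patients and 5% or 15% in issue patients (assumed), the pooled figure would be (624 × 9.5% + 184 × 5%) / 808 = 8.5%, or 10.8% with 15%.

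**6. Is a pooled table named anywhere?** SAP 9.6, 13.3 and 13.4 name none. The meta-analytic pooling in protocol 11.1.3 was dropped in SAP section 8.

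**The case against.** The strongest reply is that nothing redefines the Safety Analysis Set. SAP 9.6.1.1, 9.7.1.1 and 13.3 all keep it intact, and the restriction in 9.7.1.2 covers only confirmatory and secondary analyses. A reader might infer from section 8 that the issue patients have been removed from the safety set. The documents do not establish that; they contradict themselves. This part of the reply stands. It does not settle the matter, because 9.6.1.1 allows exceptions where indicated, section 8 names safety endpoints, and 13.4.2 lays out the tables accordingly. The patient-level set assignments, which might show how the rule was applied, were not in the text available for this review.

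Second, nothing is lost. The issue patients receive the same safety evaluation, Appendix 3 tabulates and lists them, Appendix 4 is not divided, and the SAE reporting process does not depend on the split. A reader could add two sets of counts. That is true, and it limits the seriousness.

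Third, compromised blinding can affect safety data. AEs are partly reported by patients or elicited by questioning (protocol 9.2), and causality is a yes/no judgement by the investigator (protocol 9.3.2). This stands too. It justifies showing the split, but not leaving dosed patients out of the main incidence. The higher rate of major deviations among issue patients (11.4% against 1.9%) decides nothing either way: the criteria in SAP 9.7.1.2 concern matters such as visit windows, baseline pain and compliance.

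**Conclusion.** The point holds as a contradiction about the denominator of the main safety tables, together with the absence of a named pooled AE table. It should be fixed before unblinding, but it threatens no confirmatory conclusion, since safety is analysed descriptively.

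If section 8 governs, about 88 of 387 treated Traumed patients (23%) fall outside the main incidences, and the chance of seeing a 1% AE is about 95.0% instead of 98.0%. These figures rest on planned numbers, a 2:1:1 split of the issue patients and 4% drop-out.

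Two stronger conclusions might be drawn, and the documents support neither. One is that 184 treated patients are missing. The figure of 184 counts patients identified; the number dosed is not given, and at 4% drop-out it would be about 177 (184 × 0.96 = 176.6). The other is that the trial's safety sample-size requirement fails. Under a proportional split it is still met, though with no margin; it would be narrowly missed (94.4%) if as many as 106 issue patients were on Traumed.

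**What to change.** Reconcile the passages before unblinding:

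- In SAP section 8 and 9.6.1.2, state that the restriction to non-issue patients applies to efficacy only and that the Safety Analysis Set stays as defined in 9.7.1.1.
- In SAP 13.3 and 13.4, place the AE, SAE, related-AE, exposure, vital-sign and physical-examination tables in the main report, by arm, on the full Safety Analysis Set.
- Show the same tables for issue and non-issue patients as a supportive breakdown, with the number dosed in each group by arm, so that any effect of possible unblinding on AE reporting or causality can be seen.

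The cost is short edits in four places of the SAP and one further run of the safety tables. No new data are needed and the efficacy decision is untouched. If the SAP has already been signed off, section 11 provides for describing the change, with its rationale, in the trial report.
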